8.2.5. Safety Procedures

8.2.5.1. Vital Signs

Vital signs, including temperature, sitting blood pressure, pulse, and respiration will be collected pre-dose at time points according to [Table 1](#).

8.2.5.2. Physical Examination

A thorough and complete physical examination will be performed at time points according to [Table 1](#). Care should be taken to examine and assess any abnormalities that may be present, as indicated by the patient's medical history. Medical history should include detailed cardiovascular and pancreatitis history.

8.2.5.3. Electrocardiogram

Electrocardiograms should be performed before blood is drawn during visits requiring blood draws. A standard 12-lead ECG will be performed at time points according to [Table 1](#). A 12-lead ECG should be performed in the supine position after resting for at least 10 minutes. For each ECG recording throughout the study, the electrodes should be positioned in the same place as much as possible. The ECG will be interpreted locally by the investigator. Heart rate will be recorded from the ventricular rate, and the PR, QRS, RR, QTcB and QTcF intervals will be recorded. Any clinically significant abnormality should be documented as an AE/SAE as applicable. Each ECG tracing will be analyzed in comparison with the screening record trace. The ECG strips or reports will be retained with the source.

8.2.5.4. Laboratory Testing

Hematology, chemistry, urinalysis, and serum pregnancy testing samples will be analyzed by a central laboratory. Urine pregnancy testing samples will be analyzed locally (patients will use a pregnancy test provided by the site for phone visits in the follow-up). Detailed instructions for blood sample collection are in the laboratory manual provided to study sites.

Samples for laboratory testing will be collected at visits according to [Table 1](#). Tests will include:

Blood Chemistry

Sodium	Total protein, serum	Total bilirubin
Potassium	Creatinine	Total cholesterol*
Chloride	Blood urea nitrogen (BUN)	Triglycerides
Carbon dioxide	Aspartate aminotransferase (AST)	Uric acid
Calcium	Alanine aminotransferase (ALT)	Creatine phosphokinase (CPK)
Glucose	Alkaline phosphatase	Phosphorus
Albumin	Lactate dehydrogenase (LDH)	Magnesium

*(low-density lipoprotein [LDL] and high-density lipoprotein [HDL])

Hematology

Hemoglobin	Differential:
Hematocrit	Neutrophils
Red blood cells (RBCs)	Lymphocytes
White blood cells (WBCs)	Monocytes
Red cell indices	Basophils
Platelet count	Eosinophils

Urinalysis

Color	Glucose	RBC
Clarity	Blood	Hyaline and other casts
pH	Bilirubin	Bacteria
Specific gravity	Leukocyte esterase	Epithelial cells
Ketones	Nitrite	Crystals
Protein	WBC	Yeast

Other Laboratory Tests

Samples will also be collected for assessment of LPL enzyme activity after administration of heparin at screening visit 2 and at visit 13. Other laboratory tests include HbA1C, insulin, C-peptide, Homa, inflammation biomarker panel (eg, hs-CRP, IL-1, IL-6, IL-8, and TNF α), amylase, lipase, APOC2, APOC3, APOA5, and NEFA, and lipid sub-fractions by UC.

Abnormal Laboratory Values and Laboratory Adverse Events

- All laboratory values must be reviewed by the investigator or authorized designee.
- Significantly abnormal test results that occur after start of treatment must be repeated to confirm the nature and degree of the abnormality. When necessary, appropriate ancillary investigations should be initiated. If the abnormality fails to resolve or cannot be explained by events or conditions unrelated to the study medication or its administration, the medical monitor must be consulted.
- The clinical significance of an abnormal test value, within the context of the disease under study, must be determined by the investigator.

Criteria for reporting laboratory values as an AE are provided in Section 9.4.5.

8.2.6. Pharmacokinetic and Anti-Drug Antibody Procedures**8.2.6.1. Drug Concentration Measurements and Samples**

Samples for drug concentration will be collected at time points listed in Table 1.

8.2.6.2. Anti-Drug Antibody Measurements and Samples

Serum samples for ADA assessment will be collected at time points listed in Table 1. They will be collected pre-dose on days when study drug is administered.

Patients who exhibit a treatment emergent or treatment boosted positive ADA assay response in their last sample analyzed will be followed until the titers are less than 240 or within 2 dilution steps from the pre-dose baseline titer levels.

8.2.7. Biomarker Procedures

Biomarker samples will be collected at time points according to [Table 1](#).

Lipoprotein lipase enzyme activity will be measured using the assay developed by Imamura et al, ([Imamura 2008](#)) in fasting plasma collected from patients at visit 2 (after eligibility has been confirmed by screening procedures at visit 1 and 1b and the patient has received an IV bolus of 60 IU of heparin per kg of body weight), and at visit 13 (after administration of an IV bolus of 60 IU of heparin per kg of body weight). Lipoprotein lipase is bound to the luminal side of capillary endothelium by glycosoaminoglycans and the infusion of heparin is required for the disassociation of the bound LPL into the circulation. The heparin infusion is generally considered to be safe and well tolerated.

8.2.8. Biochemical Measures of Pancreatic Health

Amylase and pancreatic lipase are clinical measures of pancreatic health, which are elevated during episodes of AP and will be measured at every visit. Levels of IL6 and CRP have been demonstrated to be elevated during AP episodes and are considered exploratory measures due to limited clinical evidence and therefore will only be measured at baseline and during the treatment period. Research samples will be collected at every visit for any post-hoc analyses of biochemical markers for correlation with clinical symptoms of AP and may include trypsinogen, pancreatic isoamylase, pancreatic elastase, serum trypsin, phospholipase A2, carboxypeptidase B.

8.2.9.1. Genomics Study

To better understand the response to inhibition of ANGPTL3 in patients with sHTG, this study will enroll patients with LPL deficiency (as assessed by genotype) as well as those with relatively intact LPL activity. Lipoprotein lipase deficiency can be caused by LOF mutations in LPL or other genes that modulate the enzymatic activity of LPL, such as APOC2, and APOA5. APOC2 serves as an activator protein of LPL and APOA5 is thought to stabilize the lipoprotein enzyme complex and enhance lipolysis.

Loss of function mutations in LPL (eg, deletions or duplications) lead to levels of undetectable LPL activity and mass in plasma ([Monsalve 1990](#)) and heterozygotes who have a G215E mutation have mean levels of LPL at about 50% of normal though individually their levels overlap with normal levels ([Wilson 1993](#)). Other genetic causes of sHTG include homozygous mutations in LMF1 and GPIHBP1, which are genes in the LPL pathway. In a study of 86 sHTG patients (both Type 1 and Type 5 with TGs > 10 mmol/L), with a range of LPL enzyme activity levels, 35% had rare causative mutations in LPL, 11% had mutations in APOA5, APOC2, LMF1 and GPIHBP1,

and the rest had either common variants in these genes or no identified mutations (Surendran 2012). Based on the data from this Dutch study, not all LOF mutations in the LPL pathway resulted in diminished LPL enzyme activity.

DNA will be collected for all patients and sequencing performed to confirm mutations if previously genotyped and analysis will be done to identify mutations in genes in the LPL pathway eg, LPL, APOC2, APOA5 as well as other genes known to be associated with sHTG.

9. SAFETY DEFINITIONS, REPORTING, AND MONITORING

9.1. Obligations of Investigator

The investigator must promptly report to the Institutional Review Board (IRB)/Ethics Committee (EC) all unanticipated problems involving risks to patient. This includes death from any cause and all SAEs related to the use of the study drug. It is recommended that all SAEs be reported to the IRB/EC, regardless of assessed causality.

9.2. Obligations of Sponsor

During the course of the study, the sponsor will report in an expedited manner all SAEs that are both unexpected and at least reasonably related to the study drug (suspected unexpected serious adverse reaction [SUSAR]), to the health authorities, IRBs/ECs as appropriate, and to the investigators.

Any AE not listed as an expected event in the Investigator's Brochure or in this protocol will be considered as unexpected. Any worsening of or new onset of symptoms related to sHTG which occur during the screening period prior to study drug administration will be considered expected.

In addition, the sponsor will report in an expedited manner all SAEs that are expected and at least reasonably related to the study drug to the health authorities, according to local regulations.

At the completion of the study, the sponsor will report all safety observations made during the conduct of the trial in the clinical study report to health authorities and IRBs/ECs as appropriate.

9.3. Definitions

9.3.1. Adverse Event

An AE is any untoward medical occurrence in a patient administered a study drug, which may or may not have a causal relationship with the study drug. Therefore, an AE is any unfavorable and unintended sign (including abnormal laboratory finding), symptom, or disease, which is temporally associated with the use of a study drug, whether or not considered related to the study drug.

An AE also includes any worsening (ie, any clinically significant change in frequency and/or intensity) of a pre-existing condition that is temporally associated with the use of the study drug.

9.3.2. Serious Adverse Event

An SAE is any untoward medical occurrence that at any dose:

- Results in **death** - includes all deaths, even those that appear to be completely unrelated to study drug (eg, a car accident in which a patient is a passenger).
- Is **life-threatening** - in the view of the investigator, the patient is at immediate risk of death at the time of the event. This does not include an AE that had it occurred in a more severe form, might have caused death.
- Requires in-patient **hospitalization** or **prolongation of existing hospitalization**. In-patient hospitalization is defined as admission to a hospital or an emergency room for longer than 24 hours. Prolongation of existing hospitalization is defined as a hospital stay that is longer than was originally anticipated for the event, or is prolonged due to the development of a new AE as determined by the investigator or treating physician.
- Results in persistent or significant **disability/incapacity** (substantial disruption of one's ability to conduct normal life functions).
- Is a **congenital anomaly/birth defect**
- Is an **important medical event** - Important medical events may not be immediately life-threatening or result in death or hospitalization, but may jeopardize the patient or may require intervention to prevent one of the other serious outcomes listed above (eg, intensive treatment in an emergency room or at home for allergic bronchospasm; blood dyscrasias or convulsions that do not result in hospitalization; or development of drug dependency or drug abuse).

9.3.3. Infusion Reactions

Infusion reactions are defined as any AE that occurs during the infusion or within 2 hours after the infusion is completed. All infusion reactions must be reported as AEs (defined in Section 9.4.1) and graded using the grading scales as instructed in Section 9.5.1.

9.4. Recording and Reporting Adverse Events

9.4.1. Adverse Events

The investigator (or designee) will record all AEs that occur from the time the informed consent is signed until the end of study. Refer to the study reference manual for the procedures to be followed.

Information on follow-up for AEs is provided in Section 9.4.6. Laboratory, vital signs, or ECG abnormalities are to be recorded as AEs as outlined in Section 9.4.5.

9.4.2. Serious Adverse Events

All SAEs, regardless of assessment of causal relationship to study drug, must be reported to the sponsor (or designee) within 24 hours. Refer to the study reference manual for the procedure to be followed.

Information not available at the time of the initial report must be documented in a follow-up report. Substantiating data such as relevant hospital or medical records and diagnostic test reports may also be requested.

In the event the investigator is informed of an SAE after the patient completes the study, the following will apply:

- SAE with an onset within 30 days of the end of study or within 24 weeks of last study drug administration if the patient terminated from the study early - the SAE will be reported to the sponsor. The investigator should make every effort to obtain follow-up information on the outcome until the event is considered chronic and/or stable.
- SAE with an onset day greater than 30 days from the end of study or 24 weeks from the early termination visit for patients who terminate from the study early - only fatal SAEs and those deemed by the investigator to be drug-related SAEs will be reported to the sponsor. The investigator should make every effort to obtain follow-up information on the outcome of a drug-related SAE until the event is considered chronic and/or stable.

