7.4.2. Study Drug Discontinuation

Patients who permanently discontinue from study drug before entering the double-blind treatment period (day 1, week 0) will be contacted to assess any adverse events (AEs) but will not be asked to return for the remaining study visits.

Patients who permanently discontinue from study drug during the double-blind treatment period will be asked to return to the clinic within 5 days for an early termination visit consisting of week 12 study assessments; these patients will then enter the off-drug treatment follow-up period.

Patients who are permanently withdrawn from study drug during the single-blind treatment period will be asked to return to the clinic for an early termination visit consisting of week 24 study

assessments. After the early termination visit, patients will enter the off-drug treatment follow-up period.

Patients who are unable or unwilling to attend the study visits as described above should still be followed for at least 24 weeks from the last dose of study drug or up to recovery or stabilization of any AE to be followed-up as specified in this protocol, whichever comes last. The assessments completed should include pregnancy testing for WOCBP. A final end of study visit should take place with assessments as specified in the end of study visit (ie, follow up visit) at 24 weeks after the premature discontinuation of study drug.

Sexually active males and WOCBP who discontinue the study prematurely should be reminded at the early termination visit following treatment discontinuation to maintain the contraceptive measures (as described in Section 6.2.2) for 24 weeks after the last dose of study drug. At this visit, WOCBP will be provided a sufficient number of urine pregnancy tests with instructions to test for pregnancy 4 weeks after this visit and every 4 weeks (Q4W) thereafter. The patient will also be notified of Q4W follow-up phone calls to confirm continued contraception use, to obtain results of urine pregnancy tests, and to obtain information on whether pregnancy has occurred in WOCBP and in female partners of male patients.

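### For early leavers, the two late-SAE rules in Protocol 9.4.2 count 24 weeks from different dates, so an onset between the two limits falls under neither

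*Protocol*

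**What the plan says.** Protocol 9.4.2 opens with a general rule: "All SAEs, regardless of assessment of causal relationship to study drug, must be reported to the sponsor (or designee) within 24 hours". It carries no end date. The section then turns to a special case, introduced by "In the event the investigator is informed of an SAE after the patient completes the study, the following will apply", and gives two bullets.

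- **First bullet, full reporting.** Every SAE goes to the sponsor if its onset is no more than 30 days past the end of study or, for early leavers, "within 24 weeks of last study drug administration if the patient terminated from the study early".
- **Second bullet, restricted reporting.** Only fatal SAEs, and those the investigator judges drug-related, go to the sponsor if onset is more than 30 days past the end of study or, for early leavers, beyond "24 weeks from the early termination visit for patients who terminate from the study early".

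The timing of the early termination visit comes from Protocol 7.4.2. A patient who stops drug in the double-blind period is asked to "return to the clinic within 5 days for an early termination visit". For the single-blind period, patients "withdrawn from study drug during the single-blind treatment period will be asked to return to the clinic for an early termination visit", and no number of days is given. Section 8.1.2 and footnotes 2 and 3 of the Schedule of Events give no number of days for either period.

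**The concern.** The two bullets are evidently meant to follow one another: report everything up to a limit, then report only the gravest or drug-related events. For that to work, the second has to begin where the first ends. For early leavers the first is counted from the last dose and the second from a visit that normally comes later, so a stretch of days lies between them.

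The literal result makes no sense as a safety rule. Suppose the early termination visit takes place 33 days after the last dose. A fatal SAE with onset 180 days after the last dose is in neither bullet, while a fatal SAE at 210 days is in the second. Nothing in the protocol explains why the middle period should be treated more leniently than the later one.

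What is at stake is whether the sponsor hears of late SAEs, including fatal and drug-related ones, in patients who have left. Two sites could read the same text differently in good faith.

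**Working it through.** The documents state no length for the uncovered period, so there is no figure of theirs to reproduce. The check is date arithmetic.

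**Inputs**

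- Both limits are 24 weeks: 24 × 7 = 168 days (Protocol 9.4.2). This agrees with the schedule: last planned dose on day 141, final visit on day 309, and 309 − 141 = 168.
- Dosing interval: 28 days (days 1, 29 and 57, then 85, 113 and 141; Protocol 7.1).
- Dosing visit window: 4 days either way (Schedule of Events).
- Early termination visit: within 5 days in the double-blind period, taken here as 5 days from the decision to stop; no deadline in the single-blind period (Protocol 7.4.2).

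**Formula**

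First limit = last dose + 168. Second limit = early termination visit + 168.

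Uncovered window = (visit + 168) − (last dose + 168) = visit date − last dose date.

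For the 33-day example, the first bullet ends at day 168 after the last dose and the second begins after day 33 + 168 = 201. Day 180 is in neither bullet; day 210 is in the second.

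**Results**

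| Case | Arithmetic | Window |
|---|---|---|
| Double-blind, stop decided on a dosing day | 0 to 0 + 5 | 0 to 5 days |
| Double-blind, stop decided 14 days after a dose | 14 + 5 | up to 19 days |
| Double-blind, stop decided at the next nominal dosing visit | 28 to 28 + 5 | 28 to 33 days |
| Same, with that visit 4 days late | 28 + 4 + 5 | up to 37 days |
| Same, with the last dose also 4 days early | 28 + 8 + 5 | up to 41 days |
| Double-blind, one dose skipped before the permanent stop | 56 + 5 | up to 61 days |
| Single-blind, last dose day 141, visit day 169 | 169 − 141 | 28 days |
| Single-blind, last dose day 85, visit as late as day 169 (assumed) | 169 − 85 | 84 days |

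**Check of the remedy**

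With one start date A in both bullets, the window is (A + 168) − (A + 168) = 0 days in every row.

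**The case against.** The strongest reply is that these bullets are not the only rules, and that they reach few patients.

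*Other rules apply.* A reader might infer that no rule at all covers the window. The documents do not support that. The opening sentence of 9.4.2 has no end date. Section 9.4.3 requires events of special interest, pancreatitis among them, to be reported within 24 hours of identification, also with no end date. Section 9.1 separately requires deaths and drug-related SAEs to go to the ethics committee. This stands in part. But the bullets address precisely the SAE learned of after the patient has left, and if the opening sentence overrode them the second bullet would restrict nothing. Section 9.4.3 refers back to 9.4.2 for its reporting process, and 9.1 does not concern reports to the sponsor. These rules may cover the window; none says that it does.

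*Stopping drug is not leaving the study.* Patients who stop drug enter off-drug follow-up (7.4.2, 8.1.2), and while they remain there the bullets do not yet apply. The scheduled follow-up runs 309 − 169 = 140 days from the week 24 visit. If the same spacing follows an early termination visit, which is an inference, the 30-day limb reaches visit + 140 + 30 = visit + 170, past the second bullet's start at visit + 168, and no gap remains. With only the minimum follow-up, that limb reaches last dose + 168 + 30 and cuts a window of 33 to 37 days to 3 to 7 days. Most of this stands and limits the point mainly to patients who leave the study itself after attending the visit. It does not remove the point: both bullets give early leavers their own limit, and 5.1.1 defines end of study as the last patient's last visit, so how the 30-day limb works for one patient is unclear.

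*Sections 7.4.2 and 8.1.2.* A reader might infer that 7.4.2 contains the same contradiction, since patients who cannot attend the planned visits "should still be followed for at least 24 weeks from the last dose of study drug" but have a final visit "at 24 weeks after the premature discontinuation of study drug". It does not. The first is a floor, and a visit 24 weeks after a later date satisfies it. Section 8.1.2 counts follow-up only from the last dose.

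*Unseen procedures.* Section 9.4.2 refers sites to a study reference manual, which may settle practice. That cannot be checked here.

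**Conclusion.** Wrong as written, low severity. The two bullets use different start dates for early leavers and do not meet whenever the early termination visit falls after the last dose. The window runs from 0 to 5 days for a stop on a dosing day to about 28 to 37 days for a stop at the next double-blind dosing visit. Longer windows need both visit windows stretched, a skipped dose or a late single-blind visit; for the last, the text sets no upper limit. These lengths assume that the 5 days run from the decision to stop and that the 30-day limb does not apply to early leavers.

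Three stronger readings are not supported:

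- *The gap is at least five weeks.* Five weeks is near the top of the usual double-blind range, and the window can be nil.
- *Ten patients are exposed (20% of 50).* The 20% drop-out in Protocol 10.2 raises 24 patients to 30 for the triglyceride analysis. It is not applied to 50, and it does not say who leaves the study after an early termination visit.
- *Known pancreatitis cases fall in the gap.* The introduction reports events 70 days or later after a single dose. That is a lower bound, well inside 168 days; no event after day 168 is reported.

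The effect on the planned analysis is also slight. SAP 4.8.1 ends the treatment-emergent period at last dose + 168 days for patients who do not go on to further dosing, so an SAE in the window would not enter those tables in any case. What is affected is late safety reporting to the sponsor.

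**What to change.** Reconcile the two bullets of Protocol 9.4.2 so that, for early leavers, both count from one date and restricted reporting starts the day after full reporting ends. The documents do not show which date was intended, so the sponsor has to choose it. No change to 7.4.2 or 8.1.2 is needed.

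The cost is one wording change at the next amendment and a note to sites. No visits, samples or analyses are added.
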